**PROCEDURES INVOLVED:**

Prospective, double-blinded, randomized clinical trial.

Randomization: Patients will be approached after repair of OASIS has been completed, and prior to the epidural catheter removal. After informed consent, eligible patients will be randomized to 1 of 3 possible paired interventions:

- 1) Epidural saline + intravenous saline
- 2) Epidural morphine 3mg + intravenous saline
- 3) Epidural morphine 3mg + intravenous ketamine 0.3mg/kg (based on pre-delivery weight)

The subjects will be randomized to a 1/5 chance for group 1 and a 2/5 chance for group 2 and group 3. Randomization and study drug preparation will be conducted by the pharmacy on Prentice 10th floor. The epidural catheter will be removed after study drug or placebo administration, and the patient will be transferred to postpartum unit following standard institutional protocol.

Post-neuraxial morphine order set will be ordered for postpartum analgesia and monitoring.

## Anesthesia OB – Post Neuraxial Morphine Order Set

Component	Order Details
MEDICATION - Communication	
The following orders indicate that the patient is to receive no sedatives or opioids except those ordered by Anesthesiology for the next 12 hours.	
 1 - No Sedatives	Start: T;N, For: 12 Hour
 1 - No Opioids Except by Anesthesia	Start: T;N, For: 12 Hour
MEDICATIONS - Oxytocin	
Update order comment and notify nurse to increase oxytocin to a maximum of 36 Units/Hour (600 mL/hour) if uterine atony continues.	
 oxytocin 30 Unit + Sodium Chloride 0.9% 500 mL	IV Infusion, Titrate Parameters: Titrate per OB Protocol, Start: 9/6/2017 10:27, Titrate per OB Protocol, 500 mL (Bag Vol)
MEDICATIONS - Pain	
 ketorolac (Toradol)	30 mg, Dose Form: Inj, IV Push, Q 6 Hours, For: 12 Hour
 acetaminophen-HYDROcodone (Norco 10 mg-325 mg oral tablet)	1 Tab, Dose Form: Tab, PO, Q 4 Hours, PRN, Pain-Mild (pain score 1-3)
 acetaminophen-HYDROcodone (Norco 10 mg-325 mg oral tablet)	2 Tab, Dose Form: Tab, PO, Q 4 Hours, PRN, Pain-Moderate (pain score 4-6)
MEDICATIONS - Multi-modal Anti-Emetics	
Choose dexamethasone only if NOT administered in the Operating Room.	
 dexamethasone (Decadron)	10 mg, Dose Form: Inj, IV Push, Once, For: 12, Hour, PRN, Nausea/Vomiting
 ondansetron (Zofran)	4 mg, Dose Form: Inj, IV Push, Q 6 Hours, For: 12, Hour, PRN, Nausea/Vomiting
 prochlorperazine (Compazine)	10 mg, Dose Form: Inj, IV Push, Once, For: 12, Hour, PRN, Nausea
MEDICATIONS -Other	
 nalbuphine (Nubain)	2.5 mg, Dose Form: Inj (PF), IV Push, Q 6 Hours, For: 12, Hour, PRN, Pruritus
 nalbuphine (Nubain)	5 mg, Dose Form: Inj (PF), IV Push, Q 6 Hours, For: 24, Hour, PRN, Pruritus
 naloxone (Narcan)	200 mcg, Dose Form: Inj, IV Push, As Needed, For: 12, Hour, PRN, CNS/Respiratory Depression
NURSING	
 Respirations	Q 1 Hour, 12 Hour
 Respirations	Q 2 Hours, 12 Hour, T;N+720
 Call Anesthesia	If respiratory rate is less than 8 per minute or in respiratory distress and naloxone is administered, if refractory to treatment.
RESPIRATORY SERVICES	
 O2 Therapy - Nasal Cannula	2 lpm

## Study timeline:

Version #: 1.5

Version Date:04/23/2019

Page 4 of 14

HRP-593 / v011017

Phase	Sequence of Events	Interventions or Assessment Variables	
I  Information will be collected during patient hospitalization	PPD 0	Checklist followed by study team member for eligibility assessment	Hypothesis testing
	Post-delivery (Following 3 rd stage of labor) Eligibility confirmed, repair of perineal laceration completed, confirmation of hemodynamic stability.	Patient approached by member of study team for informed consent Study drug randomization and administration -Demographics -Obstetrical Data -Anesthesia Data - Richmond Agitation Sedation Score – 15-30 min after intravenous drug administration - Addiction Research Center Inventory and lysergic acid (LSD) questionnaire - Plan to breastfeed. If yes, how long they plan to breastfeed? (<3 months, 3-6 months, >6 months). If multiparous, did they breastfeed in the past? If yes, for how long? When (<3 months, 3-6 months, >6 months) and why did they stop?	
	PPD 1	-Perineal pain scores (VRS) -Need for additional analgesic intake for management of perineal pain (yes or no)  • Total analgesic consumption (opiates/nsaids) - McGill Pain Questionnaire -Brief Pain Inventory (BPI) Short Form	.

II  Information will be collected in-person during patient's perineal clinic visit	PPD 2-7	
 
-Perineal pain scores (VRS)
 
-Need for additional analgesic intake for management of perineal pain (yes or no) 
 
• Total analgesic consumption (opiates/nsaids)
 
 
 
-McGill Pain Questionnaire
 
-Brief Pain Inventory (BPI) Short Form
 
-Edinburgh Postnatal Depression Scale (EPDS)
 
-Maternal Postnatal Attachment Scale (MPAS)
 
- If plan was to breastfeed, is patient currently breastfeeding? yes or no? If not, why did she stop?
 
-MEDoc pathway
 
Hot and Cold Sensory Threshold Assessment test will be performed
 
	
 
-Edinburgh Postnatal Depression Scale (EPDS), Maternal Postnatal Attachment Scale (MPAS): if perineal pain is not well –controlled, the patient will be at increased risk for depression. It will also impact the patient's ability to bond with the newborn.
 
-MEDoc device is predictive of chronic pain
 

III  Information will be collected remotely via electronic and/or printed surveys, depending on the patient's preference	6 weeks	
 
- Perineal pain scores (VRS)
 
-Need for additional analgesic intake for management of perineal pain (yes or no) 
 
• Total analgesic consumption (opiates/nsaids)
 
 
 
-McGill Pain Questionnaire
 
-Brief Pain Inventory (BPI) Short Form
 
- If plan was to breastfeed, is patient currently breastfeeding? yes or no? If not, why did she stop?
 
-Edinburgh Postnatal Depression Scale (EPDS)
 
-Maternal Postnatal Attachment Scale (MPAS)
 
-Patient Reported Outcome Measurement Information System (PROMIS) 29
 
	
IV	3 months	-Perineal pain score (VRS)	

Information will be collected remotely via electronic and/or printed surveys, depending on the patient's preference		
 
-Need for additional analgesic intake for management of perineal pain (yes or no) 
 
• Total analgesic consumption (opiates/nsaids)
 
 
 
-Physical therapy treatment (yes or no)
 
-The McGill Pain Questionnaire
 
-Brief Pain Inventory (BPI) Short Form
 
- If plan was to breastfeed, is patient currently breastfeeding? yes or no? If not, why did she stop?
 
-Edinburgh Postnatal Depression Scale (EPDS)
 
-Maternal Postnatal Attachment Scale (MPAS)
 
-Patient Reported Outcome Measurement Information System (PROMIS) 29
 
- Female Sexual Function Index (FSFI)
 
	
V	6 Months	
 
-Perineal pain score (VRS)
 
-Physical therapy treatment for pelvic pain (yes or no)
 
- If plan was to breastfeed, is patient currently breastfeeding? yes or no? If not, why did she stop? -
 
Patient Reported Outcome Measurement Information System (PROMIS) 29
 
- Female Sexual Function Index (FSFI)
 
	
VI	12 Months	
 
-Perineal pain score (VRS)
 
-Physical therapy treatment for pelvic pain(yes or no)
 
- If plan was to breastfeed, is patient currently breastfeeding? yes or no? If not, why did she stop?
 
	

		-Patient Reported Outcome Measurement Information System (PROMIS) 29 - Female Sexual Function Index (FSFI)	
--	--	---	--

Phase I will involve the collection of data points from patient interview, chart review, and surveys during the initial hospitalization. Phase II entails the administration of a brief questionnaire and surveys to the patient during their 1 week follow up appointment in the specialty perineal clinic.

Thermal pain test (threshold measurement) will be performed during the first follow up visit if the subject attends the the PEAPOD clinic. The Medoc PATHWAY Pain & Sensory Evaluation System (Medoc Ltd, Israel, Durham NC)) with advanced thermal stimulator (ATS) will be used to apply 6 thermal stimuli to participants' left volar forearm, 5cm from the wrist. The thermal baseline temperature will be set to 32°C. The Medoc system order of stimuli (3 cold and 3 warm) with a rest period between stimuli.

At the start of each trial, the thermode increases or decreases in temperature at the rate of 1°C per second and participants are instructed to push a button when the stimuli is considered painful. After participants press the button, the thermode returns to baseline temperature and the next trial begins. The participants are also given a separate shut off button which terminates the testing.

The second part of the test (summation) will include a single stimulus with the thermode set at 5°C with a 45 second timed stimulus. Subjects will use a verbal rating scale (VRS) to rate the painfulness of the stimulus at 10 second intervals (anchored with “no pain” 0 and 100 “worst pain imaginable”)

Phases III and IV will rely on the collection of patient data using a brief questionnaire and surveys at 6 weeks and 3 months postpartum.

Phases V and VI will rely on perineal pain score (VRS) responses at 6 and 12 months post-delivery.

A pre-survey notification message (via phone or email) will be sent to patients prior to phases III and IV. A personalized cover letter will be included with the surveys. Non-respondents will be contacted using combination of messages and surveys.

#### **DATA AND SPECIMEN BANKING: N/A**

#### **DATA AND SPECIMEN MANAGEMENT:**

The primary outcome of this study is the proportion of women with pain (VRS > 4, on a 0 to 10 scale) with activity at 7±3 days postpartum. Based on the study of Macarthur et.al evaluating pain following perineal injury following childbirth, we estimated that 55% of women would have pain (VRS > 4, on a 0 to 10 scale) at 7 days. We assumed an absolute reduction of 25% in pain in women receiving epidural morphine 3mg + intravenous saline compared to epidural saline +

intravenous saline, and an absolute reduction of 30% in pain in women receiving epidural morphine 3mg + intravenous ketamine 0.3 mg/kg compared to epidural saline + intravenous saline. Groups sizes of 30:60:60 will be required to detect a difference in an effect size of 0.25 (Cramér's  $\omega$ ) at a power of 0.8 and an alpha of 0.05 using  $\chi^2$  statistic. A sample of 150 subjects will be randomized using a 1:2:2 randomization to epidural saline plus intravenous saline, epidural morphine + intravenous saline, and epidural morphine + intravenous ketamine groups. We will recruit up to 160 patients to account for subjects that decline participation and lost to follow-up.

The completed data forms will be kept in folders with only the study ID number as an identifier. These folders will be placed in a secure, locked cabinet in the Office of the Section of Obstetrical Anesthesiology located in Prentice Women's Hospital 9th floor. REDcap will be used for data entry. Only study team members will have access to the data files. Data will be password protected using a Department of Anesthesiology dedicated computer which is backed up nightly by the departmental server which is located on the 5th floor Arkes Pavilion. The access is controlled by key card and password protected by the departmental data manager.

Only the study ID number will be used to identify participants during data analysis. The data will be stored in the departmental computer until the completion of the study, including the final data analysis. Members of the anesthesia team collecting these data will be educated on the process prior to approaching prospective participants. Data both electronic and paper will be destroyed 5 years after the study has been completed using current standards and vendors.

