## **BACKGROUND:**

Obstetric anal sphincter injuries (OASIS) encompass both third and fourth degree perineal tears. These tears can have a significant impact on women's quality of life in the short and long term. One of the most distressing immediate complications of this severe perineal injury is perineal pain. A study by Macarthur et al. revealed that the frequency of perineal pain for patients with OASIS was 100%, 91%, and 20% on day 1, day 7, and 6 weeks' postpartum, respectively. Perineal pain can lead to urinary retention, defecation problems, and postpartum depression in the immediate postpartum period. In the long term, women with perineal pain may have dyspareunia and altered sexual function.

Severity of acute pain after childbirth predicts not only persistent pain, but also postpartum depression. Using a Present Pain Intensity (PPI) scale, Macarthur et al. confirmed that on postpartum day 1, women with OASIS were more likely to use the words "distressing" or "worse" to describe their perineal pain compared to women with intact perineum (48% vs. 13%). Unfortunately, the recommendations for the analgesic management of women with OASIS has not been differentiated from women that undergo vaginal delivery with no trauma or lesser trauma (first and second degree perineal lacerations).

Epidural morphine has long been used for the analgesic management of patients after cesarean delivery, and has also been reported to reduce the need for oral pain medication in the first 24 hours following vaginal delivery. Ketamine, an N-methyl-D-aspartate (NMDA) and glutamate receptor antagonist that decreases central sensitization and pain memory, has also been used at low-doses for multimodal analgesic management of women after cesarean delivery. In a study by Bauchat et al., women who received ketamine reported lower pain score 2-weeks postpartum. Ketamine also has been described as having antidepressant and anti-inflammatory effects, which could mitigate the risk of postpartum depression and improve analgesia in this subset of patients.

We propose a randomized controlled trial to study the effects of three interventions (placebo, low dose intravenous ketamine plus epidural morphine, or epidural morphine alone) in women with OASIS, on acute and chronic pain as well as on patient centered outcomes.

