## **INCLUSION AND EXCLUSION CRITERIA:**

Inclusion: age >18 years of age, English-speaking, vaginal delivery (spontaneous or assisted) of a full-term fetus (>37 weeks' gestation), OASIS as assessed by obstetrical provider, functional epidural analgesia at time of delivery, patient amenable to follow-up at their obstetrician's office or at the specialty perineal clinic within the first week postpartum.

Exclusion: previous pelvic surgery, history of chronic pelvic pain, history of recurrent urinary tract infections, women with known malformations of their urinary tract, true allergies to ketamine and/or morphine, preeclampsia or hypertensive disorder at the time of delivery, obstructive sleep apnea.

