**STUDY ENDPOINTS:**

**Primary endpoint:** Perineal pain assessed by verbal rating scale (VRS) in postpartum patients within 1 week after obstetric anal sphincter injuries.

**Secondary endpoints:** Presence of postpartum depression within 1 week after delivery, assessment of maternal-infant bonding, MEDoc Pathway Device pain sensory results within 1 week after delivery, presence of postpartum depression 6 weeks after delivery, perineal pain at 6 weeks after delivery, maternal quality of life 3 months after delivery, and female sexual function 3 months after delivery, perineal pain 3,6, and 12 months after delivery.

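### The only efficacy test described is an unadjusted three-arm chi-square on VRS > 4: valid, but it uses little of the 0-10 score and neither of two likely prognostic factors

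*Combined protocol and SAP*

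**What the plan says.** There is no separate analysis section. The primary analysis has to be inferred from the sample-size paragraph under DATA AND SPECIMEN MANAGEMENT, which says: "The primary outcome of this study is the proportion of women with pain (VRS > 4, on a 0 to 10 scale". The pain meant is pain during activity, and the window is day 7 give or take 3 days. The same paragraph sizes the trial for a chi-square statistic at 30:60:60, with alpha 0.05, power 0.8 and effect size 0.25. Its assumptions are "we estimated that 55% of women would have pain (VRS > 4, on a 0 to 10 scale) at 7 days", then "We assumed an absolute reduction of 25% in pain in women receiving epidural morphine 3mg + intravenous saline", and a 30-point reduction with morphine plus ketamine. These give rates of 55%, 30% and 25%.

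STUDY ENDPOINTS lists the primary endpoint without a cut-point: "Perineal pain assessed by verbal rating scale (VRS) in postpartum patients within 1 week after obstetric anal sphincter injuries". The Study timeline collects VRS perineal pain scores at postpartum days 2-7.

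On patient mix, BACKGROUND says "Obstetric anal sphincter injuries (OASIS) encompass both third and fourth degree perineal tears", and the inclusion criteria admit "vaginal delivery (spontaneous or assisted"). The randomization text under PROCEDURES INVOLVED gives the allocation chances (1/5, 2/5, 2/5) and no stratification factor. The Study timeline lists "Obstetrical Data" without itemising it.

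The only other statistical test mentioned, chi-square or Fisher's exact, is in the safety-monitoring section.

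**The concern.** Cutting a 0-10 score at > 4 treats a fall from 9 to 5 as no change and a fall from 5 to 4 as full success. If treatment moves the whole distribution of pain, a test of the score has more power with the same women. The aim is to learn whether pain is reduced, so the score bears directly on the question. As written, nothing says how it would be analysed, and any later analysis of it would be post hoc.

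Tear grade and delivery mode both vary by design and plausibly predict pain at one week. Neither is balanced by the described randomization or used in the analysis. At stake are some efficiency and a pre-specified answer to any question about baseline imbalance in a trial with 30 women on placebo.

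**Working it through.** **1. The plan's own figure.** For a 3 × 2 chi-square (2 df, alpha 0.05) the noncentrality is λ = N·w². With N = 150 and w = 0.25, λ = 150 × 0.0625 = 9.375 and power is 0.788. Power of 0.80 needs N = 154.2. The stated 150 at 0.8 is reproduced closely.

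**2. Power at the stated rates.** Mean rate = 0.2 × 0.55 + 0.4 × 0.30 + 0.4 × 0.25 = 0.33.

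w² = [0.2 × 0.22² + 0.4 × 0.03² + 0.4 × 0.08²] / (0.33 × 0.67) = 0.0126 / 0.2211 = 0.0570, so w = 0.239.

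Power is 0.748 at N = 150 and 0.776 at N = 160.

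**3. The same trial with the full score.** The documents give no VRS standard deviation or distribution, so a model is assumed. Each woman has a latent normal or logistic value, treatment shifts its mean, and ten thresholds turn it into a 0-10 score. The shifts are set so that the chance of a score above 4 is exactly 55%, 30% and 25%. Two threshold spacings were used, with 20,000 simulated trials each at 30:60:60.

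| Latent model, spacing | Chi-square on VRS > 4 | Kruskal-Wallis on score | Gain |
|---|---|---|---|
| Normal, fine | 0.740 | 0.883 | 0.143 |
| Normal, coarse | 0.742 | 0.878 | 0.136 |
| Logistic, fine | 0.738 | 0.850 | 0.112 |
| Logistic, coarse | 0.745 | 0.844 | 0.099 |

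A separate simulation with normal scores (SD 2, 2.5 and 3) gave 0.88-0.89 against 0.74-0.75. Simulated type I error in the table's models was about 0.05 for both tests. Without covariates, the rank test is the score test of the proportional-odds model, so these figures serve for either.

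**4. Adjusting VRS > 4 for tear grade and delivery mode.** The documents give neither prevalences nor effects. Assumed: 10% fourth-degree tears and 30% assisted deliveries.

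| Odds ratios (tear grade, delivery mode) | Unadjusted power | Adjusted power |
|---|---|---|
| 1, 1 | 0.739 | 0.730 |
| 2, 2 | 0.747 | 0.751 |
| 3, 2 | 0.737 | 0.748 |
| 4, 3 | 0.758 | 0.790 |

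The gain is about 0 to 3 points when the factors are prognostic, with a loss of about 1 point when they are not.

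**5. How much could chance imbalance matter?** With a share q of fourth-degree tears, the 95% range of the difference in share between 30 placebo and 120 active women is ±1.96·√[q(1−q)(1/30 + 1/120)]. That is ±0.120 at q = 0.10 and ±0.160 at q = 0.20. At a marginal risk of 55%:

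- For q = 0.10 and odds ratio 2, risk differs by about 16 points between grades, so the shift is 0.12 × 16 ≈ 2.0 points.
- For q = 0.20 and odds ratio 4, risk differs by about 30 points, so the shift is 0.16 × 30.4 ≈ 4.9 points.

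For comparison, the 95% half-width of the placebo-active difference is 1.96·√(0.55 × 0.45/30 + 0.275 × 0.725/120) = 0.195, or 19.5 points.

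**The case against.** The strongest reply is that nothing here is wrong. Under randomization the unadjusted chi-square holds its alpha, and that already allows for chance imbalance. A responder endpoint is a legitimate choice: the cut-point is stated in advance, the 55% control rate is built on it, and the resulting proportion is easy to interpret. All of this stands, and it is why VRS > 4 should remain the headline.

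The power gain also rests on an assumed common shift, which favours tests of the whole score. If the effect were concentrated around the cut, the gain would shrink. That stands too, and the range should be read as conditional on the model. The gap between 0.25 and 0.239 in effect size is a separate sample-size matter; the comparison in step 3 does not depend on it, because both tests use the same rates.

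Four stronger readings are tempting and are not supported:

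- A reader might infer that an imbalance in tear grade would be mistaken for a treatment effect. Step 5 shows a shift of 2 to 5 points from an extreme imbalance, against planned effects of 25 to 30 points and a half-width of 19.5.
- A reader might infer that tear grade is recorded at entry. The inclusion criteria say only that the obstetrical provider assesses OASIS, and the timeline does not itemise the obstetrical data.
- A reader might quote a larger power gain from pooling both active arms against placebo. The protocol plans no such comparison.
- A reader might think that adding the score as a secondary repairs the power of the primary test. It does not.

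**Conclusion.** The point holds as one of efficiency and pre-specification, not validity. At 30:60:60 and the plan's own rates, the described test has power of about 0.75, against about 0.84 to 0.89 for a three-arm rank or ordinal test of the 0-10 score. That gain of roughly 10 to 14 points assumes a common shift on a latent normal or logistic scale. Covariate adjustment is the smaller part: about 0 to 3 points for assumed odds ratios up to 4 and 3. Its main value is that the adjusted model is fixed before anyone sees an imbalance. This is a cheap improvement that the sponsor should make before unblinding.

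**What to change.** Add a short analysis section that does the following:

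1. Keeps the proportion with VRS > 4 as the headline outcome.
2. Names a proportional-odds (or rank-based) analysis of the 0-10 score at 7±3 days as the first key secondary. It should use the same with-activity score that is dichotomised for the primary outcome.
3. Tests this secondary only after a significant primary result: first across the three arms, then each active arm against placebo. The two comparison nulls together make up the three-arm null, so this order needs no further correction for the two comparisons.
4. Confirms that tear grade (third or fourth) and delivery mode (spontaneous or assisted) are captured under "Obstetrical Data", and itemises them on the data form if they are not.
5. Once confirmed, includes both as covariates in the score model and in a logistic model for VRS > 4. The logistic model is reported as standardized risk differences, each active arm against placebo, with 95% CIs. The unadjusted chi-square is also reported, and the plan says in advance which of the two decides the primary result.

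The cost is analysis wording, slightly more analysis work, a proportional-odds assumption to examine, and a negligible loss of power if the covariates turn out not to be prognostic. No extra patients or visits are needed.

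### The plan's own pain rates at 1:2:2 allocation give an effect size of 0.239 and about 75% power with 150 evaluable women, not 0.25 and 80%

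*Combined protocol and SAP*

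**What the plan says.** The sample-size text is in the section DATA AND SPECIMEN MANAGEMENT. It defines a binary primary outcome, assessed one week after delivery with a window of 3 days either side: "The primary outcome of this study is the proportion of women with pain (VRS > 4, on a 0 to 10 scale) with activity". It then sets the planning rates:

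- Saline arm: "we estimated that 55% of women would have pain (VRS > 4, on a 0 to 10 scale) at 7 days".
- Morphine arm: "We assumed an absolute reduction of 25% in pain in women receiving epidural morphine 3mg + intravenous saline", relative to saline.
- Morphine plus ketamine arm: "an absolute reduction of 30% in pain in women receiving epidural morphine 3mg + intravenous ketamine 0.3 mg/kg", also relative to saline.

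The conclusion follows directly: "Groups sizes of 30:60:60 will be required to detect a difference in an effect size of 0.25", labelled Cramér's ω, at power 0.8 and alpha 0.05 using the chi-square statistic. The paragraph randomizes 150 women 1:2:2 and allows up to 160 to be recruited, to cover refusals and loss to follow-up. PROCEDURES INVOLVED gives the same allocation (1/5, 2/5, 2/5). The document does not show how 0.25 was obtained from the rates.

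**The concern.** For a chi-square test across three groups, the effect size is fixed by the three rates and the allocation. It cannot be chosen separately once those are stated. The paragraph gives all of these inputs, so 0.25 can be checked, and it does not match them. The mismatch flatters the design, because noncentrality grows with the square of the effect size.

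This is the only power justification in the document, and it concerns the primary outcome. The IRB, the monitoring board and later readers would take from it a type II error of 0.20 at the planned effect. If the true figure is nearer 0.25, a non-significant result carries less evidence against the planned effect than the protocol implies.

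**Working it through.** **Inputs** (all from DATA AND SPECIMEN MANAGEMENT)

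- Rates: saline 0.55; morphine 0.55 − 0.25 = 0.30; morphine + ketamine 0.55 − 0.30 = 0.25
- Allocation weights: 0.2, 0.4, 0.4 (30:60:60)
- N = 150, alpha = 0.05
- Test: chi-square on a 3 × 2 table, so df = (3 − 1)(2 − 1) = 2. For such a table Cramér's coefficient equals w, so the label creates no ambiguity.

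**Step 1: the plan's own figure.** Taking w = 0.25 as given, noncentrality = N·w² = 150 × 0.0625 = 9.375. Power from the noncentral chi-square on 2 df is 0.788, and the N for 0.80 is 154.2, so 155. The paragraph's last step is therefore reproduced to the one decimal it states.

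**Step 2: effect size from the stated rates.**

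- Pooled rate = 0.2 × 0.55 + 0.4 × 0.30 + 0.4 × 0.25 = 0.33
- w² = Σ aᵢ(pᵢ − p̄)² / [p̄(1 − p̄)]
- Numerator = 0.2 × 0.22² + 0.4 × 0.03² + 0.4 × 0.08² = 0.00968 + 0.00036 + 0.00256 = 0.01260
- Denominator = 0.33 × 0.67 = 0.2211
- w² = 0.0570, so w = 0.2387

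**Step 3: power at the stated rates.** Noncentrality = 150 × 0.0570 = 8.55, against 9.375 in Step 1.

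| Evaluable women (1:2:2) | Noncentral chi-square | Exact enumeration, Pearson |
|---|---|---|
| 150 (30:60:60) | 0.748 | 0.743 |
| 160 (32:64:64) | 0.776 | 0.772 |
| 170 (34:68:68) | 0.80 (solved N = 169.1) | 0.795 |

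**Step 4: loss to follow-up.** The plan gives no dropout rate. Assuming 5% to 15% loss from 160, 152 to 136 women are evaluable and power is 0.754 to 0.703. If the extra 10 exactly replace losses, it is 0.748.

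**Step 5: other readings that might yield 0.25.**

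- Equal groups (50:50:50) at the same rates: w = 0.272, power 0.857. This is not the design. It shows that, at these rates, the 1:2:2 split is what takes 150 women below 0.80.
- Unweighted mean rate (0.367) as the null value: w = 0.245, which does not fit 1:2:2.
- Reductions read as relative: w = 0.125, power 0.258.
- One degree of freedom with w = 0.239: power 0.832, but 1 df is wrong for three groups.
- Control rate 50% with the same absolute reductions (50/25/20%): p̄ = 0.28 and w² = 0.0126 / (0.28 × 0.72) = 0.0625, so w is exactly 0.25. This may be the source, but the document states 55%.

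**The case against.** Four points can be made for the plan.

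1. The sentence about 0.25 is not itself false: at w = 0.25, 150 women give 0.788, which rounds to 0.8. This stands. The 150 versus 155 difference alone would be a rounding matter. The fault lies between the rates and the 0.25.
2. The document never says that 0.25 was calculated from the rates. True, but the rates come immediately before it and are put to no other use. If 0.25 is a separate target, the paragraph plans on two different effects and still has to be reconciled.
3. The gap is small beside the uncertainty in the assumptions: a control rate of 57% with 30% and 25% in the other arms would bring power at 150 to 0.80. This is fair as a comment on size. It does not make 0.80 the power at the rates the plan chose.
4. Some two-group contrasts reach 80% at alpha 0.05 with the same 150 women: saline against morphine plus ketamine 0.803, and saline against both morphine arms pooled 0.809. However, the paragraph powers a chi-square effect size across the three groups and names neither contrast as the powered test. Saline against morphine alone has 0.633.

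It is also fair that stated power does not enter the final inference. No estimate, type I error or safety provision changes, and a careful reader would judge a null result mainly by its confidence intervals.

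**Conclusion.** The concern holds. At the plan's stated rates and allocation, w is 0.239 rather than 0.25, and the overall three-group test has about 75% power at 150 evaluable women rather than 80%. The type II error is 0.25 instead of 0.20. The recruitment ceiling of 160 does not close the gap: power is 0.776 with no losses at all, and those 10 places are set aside for refusals and losses.

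The result rests on the 55/30/25% rates read as absolute differences, 1:2:2 allocation, alpha 0.05 and the Pearson chi-square on 2 df, all as the document states them. Exact enumeration agrees to within half a percentage point at 150, so the approximation is not the cause. How 0.25 arose cannot be settled from the document. The error is moderate and the design remains usable, but the statement is wrong as written.

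**What to change.** Rewrite the sample-size paragraph so that the effect size follows from the rates: under 55%, 30% and 25% with 30:60:60 evaluable women, w is about 0.24 and the 2-df chi-square test has power of about 0.75 at alpha 0.05. State the assumed loss to follow-up, and make clear whether 150 means randomized or evaluable women. If a different control rate was intended, give that rate and its basis instead.

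This costs one paragraph of wording, no extra patients, and a stated power about 5 points less favourable.

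If 0.80 is to be kept, there are two routes, each a larger decision than the correction:

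- Raise the evaluable number to about 170 (34:68:68), before any allowance for losses. Exact power there is 0.795, so a small margin above 170 is sensible.
- Prespecify the 1-df comparison of both morphine arms pooled (27.5%) against saline as the primary test, which has power of about 0.81 with the same 150 women. The hypothesis in OBJECTIVES, which covers morphine with or without ketamine, is compatible with this. It changes the primary test, so it needs its own justification and must be fixed before unblinding.

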## **OBJECTIVES:**

To assess the incidence of perineal pain in postpartum patients 1 week after obstetric anal sphincter injuries (OASIS).

We hypothesize that perineal pain at 1 week postpartum will be reduced by the administration of epidural morphine with or without intravenous ketamine after OASIS compared to on-demand analgesic management.

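### The plan's own pain rates at 1:2:2 give an effect size of 0.239 and power of about 0.75, not the stated 0.25 and 0.80; correcting the figures or moving to 2:3:3 would resolve it

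*Combined protocol and SAP*

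**What the plan says.** All references are to the combined protocol and SAP.

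- **Outcome.** Data and Specimen Management defines a binary outcome by a score threshold: "The primary outcome of this study is the proportion of women with pain (VRS > 4, on a 0 to 10 scale". The score is for pain during activity, taken about a week after delivery (day 7, give or take 3).
- **Planning rates, same section.** For saline, "we estimated that 55% of women would have pain". For morphine alone, "We assumed an absolute reduction of 25% in pain in women receiving epidural morphine 3mg + intravenous saline" relative to saline. For the third arm, "an absolute reduction of 30% in pain in women receiving epidural morphine 3mg + intravenous ketamine 0.3 mg/kg" relative to saline. The implied rates are 55%, 30% and 25%.
- **Sizing claim, same section.** Groups of 30:60:60 are said to be needed "to detect a difference in an effect size of 0.25" with power 0.8, alpha 0.05 and a chi-square statistic. Recruitment may go up to 160 to cover women who decline or are lost; no loss rate is given.
- **Allocation.** Data and Specimen Management sets the ratio: "A sample of 150 subjects will be randomized using a 1:2:2 randomization to epidural saline plus intravenous saline", with the two active arms taking the larger shares. Procedures Involved agrees: "The subjects will be randomized to a 1/5 chance for group 1 and a 2/5 chance for group 2 and group 3".
- **Hypothesis.** Objectives expects less pain with epidural morphine "with or without intravenous ketamine after OASIS compared to on-demand analgesic management", so the saline arm is the reference for both active arms.

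The documents give no reason for choosing 1:2:2.

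**The concern.** The effect size in a chi-square power calculation is not a free input once the rates and the allocation are fixed; it follows from them. The plan states all three, so they can be checked against one another, and they do not agree. The expected signal lies almost wholly between saline and the two active arms (25 and 30 points), while the active arms are expected to differ by 5 points. A small saline share therefore pulls the effect size down, and at 20% on saline it falls below 0.25.

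At stake is the probability that the primary analysis detects the effect the investigators planned for. If the rates are right, the risk of missing it is about one in four rather than one in five, and recruiting to the ceiling with no losses does not close the gap.

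**Working it through.** **Inputs.** Rates p = 0.55, 0.30, 0.25; shares s = 0.2, 0.4, 0.4; N = 150; alpha 0.05; all from the sections cited above. Degrees of freedom are not stated; 2 is assumed, from a table of three arms by two outcomes.

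**Formulas.** p̄ = Σ s·p. w = √[Σ s·(p − p̄)² / (p̄(1 − p̄))]. Power = P(noncentral chi-square on 2 df with noncentrality N·w² exceeds 5.991).

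**1. The plan's figure, from its stated effect size.** With w = 0.25 and N = 150, N·w² = 150 × 0.0625 = 9.375 and power is 0.788. That is within about a point of 0.80; a full 0.80 needs N = 155. So the stated power follows approximately if w = 0.25 is accepted.

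**2. The effect size from the plan's rates at 1:2:2.**
- p̄ = 0.2 × 0.55 + 0.4 × 0.30 + 0.4 × 0.25 = 0.33
- Σ s·(p − p̄)² = 0.2 × 0.0484 + 0.4 × 0.0009 + 0.4 × 0.0064 = 0.0126
- p̄(1 − p̄) = 0.33 × 0.67 = 0.2211
- w² = 0.0126 / 0.2211 = 0.0570, so w = 0.239

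**3. Power at that effect size.**
- N = 150 (30:60:60): N·w² = 8.55, power 0.748 (0.743 by exact enumeration of the Pearson test over three binomials)
- N = 160 (32:64:64): N·w² = 9.12, power 0.776 (exact 0.772)
- Power 0.80 needs N·w² of about 9.635: 9.635 / 0.0570 is about 169, and 170 is the first whole number to pass

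**4. The same rates at 2:3:3.**
- p̄ = 0.25 × 0.55 + 0.375 × 0.30 + 0.375 × 0.25 = 0.34375
- Σ s·(p − p̄)² = 0.25 × 0.04254 + 0.375 × 0.00191 + 0.375 × 0.00879 = 0.01465
- p̄(1 − p̄) = 0.34375 × 0.65625 = 0.22559
- w² = 0.0649, so w = 0.255

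| Evaluable N at 2:3:3 | Power |
|---|---|
| 160 (40:60:60) | 0.83 |
| 150 | 0.80 |
| 144 | 0.79 |
| 140 | 0.78 |
| 135 | 0.76 |

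The smallest N for 0.80 is 149. In whole women, 38:56:56 gives 0.807 (exact 0.804) and 37:57:56 gives 0.801 (exact 0.800). Equal allocation at 150 would give 0.857 (exact 0.861).

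**5. Pairwise power, two-sided 0.05, no adjustment for multiple comparisons.**

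| Comparison | 30:60:60 | 38:56:56 | 40:60:60 |
|---|---|---|---|
| Saline v morphine | 0.63 | 0.68 | 0.71 |
| Saline v morphine + ketamine | 0.80 | 0.84 | 0.87 |
| Morphine v morphine + ketamine | 0.09 | 0.085 | 0.09 |

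**The case against.** The strongest reply is that the ratio is a legitimate choice. Group 1 receives saline by both routes after a severe tear, and limiting the number of such women is a common reason to accept lower efficiency. The documents do not state this motive, but their silence does not make 1:2:2 wrong. A reader might infer from the figures that the allocation itself is the flaw. The documents do not support that. What is wrong is the stated effect size and power, and the ratio is one of several things that could change. Preferring 2:3:3 to the more powerful 1:1:1 also rests on limiting the number on saline, which is the consideration that could justify 1:2:2.

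A reader might also infer that the larger active arms buy nothing. On the primary outcome that is nearly so, with about 9% power to separate them. But the protocol also lists depression, bonding, thermal testing and pain to 12 months, and compares safety data between groups. It gives no planned effects for these, so their value cannot be judged from the primary outcome.

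Finally, 0.25 may be only a rounding of 0.239. That would explain the discrepancy without removing it: 0.25 itself gives 0.788 at 150, and the rates give about 0.75.

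**Conclusion.** The sizing statement is internally inconsistent. With the plan's rates and ratio, w is 0.239 and power is about 0.75 at 150 evaluable women, some 5 points below the claim. It is still only 0.78 at the ceiling of 160. This rests on a 2-df Pearson chi-square, the three planning rates being true, and every counted woman having the primary outcome.

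The 2:3:3 ratio restores the stated power for the overall three-group test, but narrowly, and only if about 150 women are evaluable: 10 losses from 160 is 10/160, about 6%. It would be too much to conclude that 2:3:3 adequately powers the comparisons named in the hypothesis. Saline versus morphine alone stays at about 0.68 to 0.71, even unadjusted.

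**What to change.** Either of two changes makes the plan consistent.

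1. **Keep 1:2:2.** Under Data and Specimen Management, replace the effect size with 0.239 and the power with 0.75 at 150 evaluable women (0.78 at 160), and add the reason for the ratio. The cost is a text change and an openly lower power.
2. **Change to 2:3:3**, if the sponsor accepts more women on saline. Amend the allocation under Procedures Involved (to 1/4, 3/8, 3/8) and under Data and Specimen Management. State that rates of 55%, 30% and 25% give w = 0.255, with power 0.80 at 150 evaluable and 0.83 at 160. At the existing ceiling this is 40:60:60, so each active arm keeps its planned 60. The cost is an amendment, a new pharmacy randomization table and about 8 more women on saline (40 instead of 32 of 160, or 38 instead of 30 of 150). If the total is held at 150, the active arms fall to 56 each.

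In either case, state the loss to follow-up that the allowance of 10 is meant to absorb. If women have already been randomized at 1:2:2, the gain from the second option shrinks with each of them, and the analysis should be stratified by allocation period.
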